3.5.3 Clear Day

A clear day will be defined as a day in which the patient reports:

- Reported “No” to having a headache in the past 24 hours AND
 - Reports no residual symptoms between headaches AND
 - Reports no “warning” symptoms prior to a headache

4 Analysis Sets

The following analysis sets will be used for evaluation of the data:

- All patients randomized set (APRS) – all patients randomized to the eptinezumab and the other advanced migraine treatment arms
- All patients treated set (APTS) – all patients in the APRS who received at least one dose of eptinezumab or other advanced migraine therapy
- Full analysis set (FAS) – all patients in the APTS who completed at least one daily report after receiving eptinezumab or other advanced migraine therapy

Effectiveness analyses over the 24-week period will be based on the FAS. We will also evaluate baseline characteristics based on the APRS to assess the validity of the randomization strategy.

Safety analyses will be based on the APTS.

5 Descriptive Statistics

All assessment data, including demographics, will be summarised using descriptive techniques. Summary statistics (n, mean, standard deviation, median, lower and upper quartiles, minimum and maximum values) will be presented for continuous variables. Counts and percentages will be presented for categorical and binary variables.

6 Patient Disposition

6.1 Summary of Patient Disposition

Participant disposition will be reported overall and by treatment group. If needed, further tables summarizing disposition by site and treatment group can be added.

6.2 Withdrawals

For each period, the number of participants who withdrew from the study, will be summarized by treatment group, and primary reason for withdrawal, and by treatment group and all reasons for withdrawal.

If relevant, Kaplan-Meier failure plots of time to withdrawal in each period will be presented by treatment group. Participants who reach the end of follow-up without withdrawing from the study will be regarded as censored.

7 Demographics and Baseline Characteristics

Demographics; baseline characteristics (including baseline eDiary compliance); baseline disease characteristics; and baseline efficacy (i.e., MMD) variables will be summarized at Baseline by randomization group and study site.

8 Recent and Concomitant Medication

Concomitant medication is any medication other than the investigational medicinal products (IMPs) that are taken during the study from Screening up until the participant completes the study at Visit 8. This includes all prescription and OTC medications, as well as vitamins and

supplements. In addition, if a patient receives a COVID-19 vaccination while enrolled in the trial, each dose of the vaccine received should be entered as a concomitant medication.

Details of all concomitant medication being taken at the time of the Screening Visit must be recorded in the eCRF at the first visit. Any changes (including reason for changes) in concomitant medication must be recorded at each subsequent visit.

For any concomitant medication for which the dose was increased due to worsening of a concurrent disorder after enrollment in the study, the worsening of the disorder must be recorded as an adverse event and the medication with the increase dosage should be reported as a new concomitant medication.

For any concomitant medication initiated due to a new disorder after enrolment in the study, the disorder must be recorded as an adverse event.

9 Exposure

For each period, the total number of infusions (for eptinezumab) or injections (for onabotulinumtoxinA) received and total number completed as planned will be summarized by treatment group.

For participants randomized to the subcutaneously injected aCGRPs, dispensing information will be obtained from the speciality pharmacy providing the medication. The date the participant reported injecting the medication will be captured in the eDiary. The information that the participant has been dispensed medication will be reported by medication group. Similarly, the information that the participant has injected the medication will be reported by medication group.

10 eDiary Compliance

Participant compliance with eDiary use will be measured between the Screening and Baseline visits. This will be used in analysis as a model covariate to adjust for expected compliance. After Baseline, all data reported through the eDiary will be used in analysis as described in the section on Section 18 Details on Data Handling.

11 Effectiveness Analysis

11.1 Overview

All effectiveness analyses will be based on the FAS, unless specified otherwise, and patients will be analyzed according to the randomized group. Details of calculating values for outcome variables and assumptions regarding handling of missing data is described in section 18.

11.2 Analysis Methodology for the Exploratory Endpoints

11.2.1 Estimand for the Number of Good Days (Week 1-4, 1-12, and 1-24) and Exploratory Endpoints

A summary of the intercurrent events that will be addressed and the estimand attributes can be found below.

The estimand is the difference in the mean weekly number of good days within each specified time interval between eptinezumab compared to other advanced preventive therapies (erenumab, fremanezumab, galcanezumab, or onabotulinumtoxinA) in adults with migraine on concomitant acute migraine therapy who have failed ≥ 2 prior oral preventive therapies and who are naïve to advanced migraine therapy based on a treatment policy strategy in which patients are analyzed according to the randomized group and are included in the analysis regardless of discontinuation or switching of the index migraine therapy during the follow-up period.

Intercurrent events that will be addressed include:

- Discontinuing the index preventive migraine medication with or without initiation of a new preventive therapy (i.e., a treatment switch).
- Withdrawal from the study due to lack of efficacy, adverse event, participant request, physician request, or loss to follow-up.
- Interruption or termination of infusions.

Attributes of the estimand for the number of good days include:

- The index treatment of interest is eptinezumab (100 mg or 300 mg) compared to other advanced preventive therapies (erenumab 70 mg or 140 mg, fremanezumab 225 mg or 675 mg, galcanezumab 120 mg, and onabotulinumtoxinA 155 units)
- The population is all patients with migraine who fulfil the inclusion and exclusion criteria.
- The primary endpoint of interest is the mean number of good days across weeks 1-12 after randomization
- The population-level summary is the mean difference between eptinezumab and other advanced preventive therapies for the endpoint

Estimands for the remaining exploratory endpoints can be formulated similarly to the estimand for the number of good days described above.

EQ-5D (weeks 1-4, 1-12, and 1-24)

- The endpoint to be obtained is the weekly EQ-5D score in each specified time interval
- The population level summary is the difference in mean weekly EQ-5D score in patients on eptinezumab relative to advanced migraine therapies in each time interval

PI-MBS (weeks 1-4, 1-12, and 1-24)

- The endpoint to be obtained is the weekly most bothersome symptom and associated severity
- The population level summary is the weekly proportion of most bothersome symptoms and average severity of each symptom in patients on eptinezumab and advanced migraine therapies in each time interval

Cumulative healthcare resource use (HCRU) (weeks 1-4, 1-12, and 1-24)

- The endpoint to be obtained is the cumulative HCRU (stratified by medical and pharmaceutical HCRU) in each specified time interval
- The population-level summary is the difference in mean HCRU in patients on eptinezumab relative to advanced migraine therapies in each time interval

HIT- 6 change from baseline score (week 4, 12, and 24)

- The endpoint to be obtained is the HIT-6 change from baseline score at each specified time point
- The population level summary is the difference in mean HIT-6 change from baseline score in patients on eptinezumab relative to advanced migraine therapies at each time point

MIDAS change from baseline score (weeks 12 and 24)

- The endpoint to be obtained is the MIDAS change from baseline score at each specified time point
- The population level summary is the difference in mean MIDAS change from baseline score in patients on eptinezumab relative to advanced migraine therapies at each time point

TSQM score (week 24)

- The endpoint to be obtained is the TSQM score at week 24 for each domain
- The population level summary is the difference in mean TSQM score in patients on eptinezumab relative to advanced migraine therapies for each domain

Switching of index medication (weeks 1-12 and 1-24)

- The endpoint to be obtained is a binary outcome indicating if a patient discontinued the index therapy and initiated a new therapy in the specified time intervals
- The population-level summary is the odds ratio of switching from the index medication in patients on eptinezumab relative to advanced migraine therapies in each time interval

SDMQ-9 (screening and week 24)

- The endpoint to be obtained is the SDMQ-9 score at each specified time point
- The population level summary is the mean SDMQ-9 in patients on eptinezumab and advanced migraine therapies in each time interval

SURE score at screening

- The endpoint to be obtained is the SURE test score at screening
- The population level summary is the mean SURE test score in patient on eptinezumab and advanced migraine therapies at screening

PAM-10 score (screening, week 12 and 24)

- The endpoint to be obtained is the PAM-10 score at each specified time point
- The population level summary is the mean PAM-10 score in patients on eptinezumab and advanced migraine therapies in each time interval

ISS score (screening, week 12 and 24)

- The endpoint to be obtained is the score or item response for each item in the ISS at each specified time point
- The population level summary is the mean ISS score or proportion of responses for each item in patients on eptinezumab at each time point

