7. **Treatment Satisfaction Questionnaire for Medication (TSQM):** The participants reported satisfaction with treatment will be evaluated at the study closeout visit (i.e., visit #9). This will be compared between randomization groups at week 24
8. **Medication Switching:** The frequency of switching of migraine preventive medication from the medication administered at baseline will be compared between the randomization groups from baseline to week 24.

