#### **6.3.1 Change in Treatment**

Participants may switch to an alternative preventive treatment in either treatment cohort after they have received their initial treatment with the medication to which they were randomized. Such a decision may be made upon recommendation of their treating clinician or participant preference. The site staff will investigate the reason for treatment change with both the treating clinician and participant. The use of medications, including gepants, for relief of acute migraine symptoms in either treatment arm is permitted and will be recorded in the smartphone application.

For all participants, the treatment to which they are initially assigned must be the treatment given at Baseline (Visit 2). Switching of medication is not permitted prior to administration of the first dose of medication. For participants who receive eptinezumab or Botox as their initial treatment and elect to switch to a subcutaneous anti-CGRP injectable (i.e., erenumab, fremanezumab or galcanezumab), they may not do so until week 12 (visit 5), after the treatment window for their initial treatment has ended. Participants who receive eptinezumab or Botox at week 12 (Visit 5) will not be permitted to switch their treatment for the remaining duration of the study.

Participants initially treated with a subcutaneous anti-CGRP injectable may only switch to eptinezumab, or Botox at week 12 (visit 5) due to the design of the study. However, these participants may switch to another of the subcutaneous anti-CGRP injectable medications at any time, once the treatment window for their previous injection has ended.

No changes in treatment will be permitted after Visit 7.

All changes in treatment are to be documented in the eCRF.

If a participant wishes to switch their medication, but does not meet the specified criteria to do so, as stated above, they should be withdrawn from the study and be treated as per standard of care by their physician.

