3.4 Definition of Planned versus Actual Treatment

As this is a pragmatic real-world study, there is no restriction on treatment pathways following randomization with the exceptions defined below. Note that all participants will be analyzed on an "intention to treat" basis, regardless of changes made to their treatment following the Baseline visit.

Participants may switch to an alternative preventive treatment in either treatment cohort after they have received their initial treatment with the medication to which they were randomized. Such a decision may be made upon recommendation of their treating clinician or participant preference. The site staff will investigate the reason for treatment change with both the treating clinician and participant. The use of medications, including gepants, for relief of acute migraine symptoms in either treatment arm is permitted and will be recorded in the smartphone application.

For all participants, the treatment to which they are initially assigned must be the treatment given at Baseline (Visit 2). Switching of medication is not permitted prior to administration of the first dose of medication. For participants who receive eptinezumab or Botox as their initial treatment and elect to switch to a subcutaneous aCGRP injectable (i.e., erenumab, fremanezumab or galcanezumab), they may not do so until week 12 (visit 5). Participants who receive eptinezumab or Botox at week 12 (Visit 5) will not be permitted to switch their treatment for the remaining duration of the study.

Participants initially treated with a subcutaneous aCGRP injectable may only switch to eptinezumab, or Botox at week 12 (visit 5) due to the design of the study. However, these participants may switch to another of the subcutaneous aCGRP injectable medications at any time, once the treatment window for their previous injection has ended.

No changes in treatment will be permitted after Visit 7.

All changes in treatment are to be documented in the eCRF.

If a participant wishes to switch their medication but does not meet the specified criteria to do so, as stated above, they should be withdrawn from the study and be treated as per standard of care by their physician.

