The difference in mean TSQM score for each domain (effectiveness, side effects, convenience, and overall satisfaction) at week 24 will be estimated using an ordinary least

square model. Independent variables will include a treatment indicator (eptinezumab vs other advanced therapies) and a vector of covariates identified to be significantly different between treatment groups after randomization. The hypothesis tested will be that the treatment term is significantly different from zero using a two-sided test at $p<0.05$. The population level summary will be the difference in mean TSQM score at week 24.

Index drug switching (weeks 1-12, and 1-24)

The difference in the odds of index drug switching will be estimated using a logistic regression model. Independent variables will include a treatment indicator (eptinezumab vs other advanced therapies) and a vector of covariates identified to be significantly different between treatment groups after randomization. The hypothesis tested will be that the treatment term is significantly different from zero using a two-sided test at $p<0.05$. The population level summary will be the odds ratio of index drug switching in the eptinezumab group relative to other advanced therapies. The analysis will be conducted weeks 12 and 24.

SDMQ-9 (screening and week 24)

The average SDMQ-9 score will be calculated for each treatment group and descriptively compared at screening and week 24.

SURE score at screening

The average SURE score will be calculated for each treatment group and descriptively compared at screening.

PAM-10 score (screening, week 12 and 24)

The average PAM-10 score will be calculated for each treatment group and descriptively compared at screening, week 12, and week 24.

ISS score (screening, week 12 and 24)

The ISS score or item responses will be analyzed descriptively using averages and proportions in the eptinezumab group at screening, week 12, and week 24.

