As would be expected in a pragmatic trial, the sample size of EVEC (100 persons per arm) is a function of the project budget and timeliness. In [Panel 6](#) we illustrate the expected power based upon the assumptions developed from PROMISE 1 and 2. We have highlighted the 100 per arm for the PROMISE 2 effect size. If, as expected, we meet the PROMISE 2 assumptions, we will have at least 72% power to demonstrate a standardized effect of 0.45. Given that we believe that the effect size will be larger in EVEC than observed in PROMISE 2, even as we pool patients with episodic and chronic migraine, we expect to have a practical power in excess of 80% to find a difference between eptinezumab and the other advanced preventive medications with an alpha of 0.05.

16 Statistical Software

Analyses will be conducted using SAS[®], Version 9.4 or later and R[®], Version 4.2.1 or later.

17 Changes to Analyses Specified in the Protocol

N/A

18 Details on Data Handling

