18.9 Drug Switching

Drug switching will be based on monthly follow-up visits. In the case in which follow-up data is missing and it is unknown whether the patient received their treatment or switched, we will assume that the patient is still receiving their index therapy.

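### The week-24 switching odds ratio compares arms with unequal permission to switch, and can fall below 1 even when the drugs are equal

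*SAP*

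**What the plan says.** Protocol Section 2, item 8, sets the objective: "The frequency of switching of migraine preventive medication from the medication administered at baseline will be compared between the randomization groups". That is a product-level definition, so a change from one SC drug to another counts. SAP Section 17, "Changes to Analyses Specified in the Protocol", is marked not applicable, so the SAP declares no departure from it. SAP 11.2.1 adds that a new therapy must have been started: "The endpoint to be obtained is a binary outcome indicating if a patient discontinued the index therapy and initiated a new therapy". In SAP 11.2.2, "The difference in the odds of index drug switching will be estimated using a logistic regression model", with a treatment indicator and any covariates found to differ between groups, tested two-sided at 0.05.

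The switching rules are in Protocol 6.3.1 and SAP 3.4:

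- For users of SC drugs, "these participants may switch to another of the subcutaneous anti-CGRP injectable medications at any time", once the window of the previous injection has ended.
- SC users "may only switch to eptinezumab, or Botox at week 12 (visit 5) due to the design of the study".
- Eptinezumab and Botox users may not move to an SC drug before week 12. If dosed at week 12, they may not switch for the rest of the study.
- No change is allowed after Visit 7. Anyone wanting a change outside these rules is withdrawn (also Protocol 6.1).

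SAP 3.3 collects nothing new after withdrawal apart from the withdrawal visit and adverse-event follow-up. SAP 18.9 covers participants without follow-up data: where "it is unknown whether the patient received their treatment or switched, we will assume that the patient is still receiving their index therapy".

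**The concern.** The odds ratio depends partly on who was permitted to switch and on which exits are recorded as switches. The free route is SC-to-SC change on monthly dosing, and only the comparator arm has it. A restricted participant who wants to change early must either wait for week 12 or leave. Someone who leaves and starts the new drug after the last contact does not meet the SAP 11.2.1 definition, and SAP 18.9 can score that person as still on index therapy. The restricted windows cover all of the eptinezumab arm but only part of the comparator arm. The uncounted exits therefore fall more heavily on eptinezumab and make it look less often abandoned.

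The intercurrent-event list in SAP 11.2.1 gives only general withdrawal reasons (lack of efficacy, participant request, physician request and similar). There is no dedicated code for withdrawal in order to switch. At stake is a between-group comparison that could be misread as better persistence on eptinezumab.

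**Working it through.** The documents state no switching rate, odds ratio or power for this endpoint, so there is no planned figure to reproduce. The check asks what the odds ratio would be if every drug were equally likely to be abandoned.

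**From the documents.** 100 per arm (SAP 15.1). Monthly means 28 days (Protocol 6.2). The last permitted change is at Visit 7, day 140 (Protocol 6.3.1, 8.7). Occasions to switch are therefore days 28, 56, 84, 112 and 140. Under 3:2:1 allocation, Botox is 1/3 of chronic-migraine comparators. If half the sample has chronic migraine (assumed), Botox is 1/2 × 1/3 = 1/6 of comparators.

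**Assumed.** Wish to switch h = 0.05 per 28 days in every arm, q = 1 − h = 0.95. w is the share of blocked would-be switchers who withdraw, with none of those exits captured; the rest wait for day 84, or stay on treatment if the wish comes later. s is the share of SC wishes that are for another SC drug. g is the share of SC users on quarterly fremanezumab, who have only the day-84 window. f = s(1 − g).

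**Formulas for counted switching by week 24.**

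- Blocked: (1 − w)(1 − q²) + q²h. With w = 0: 0.0975 + 0.9025 × 0.05 = 0.1426. With w = 0.5: 0.0488 + 0.0451 = 0.0939.
- Free: 1 − q⁵ = 0.2262.
- Eptinezumab = blocked. Comparator = 5/6 × [f × free + (1 − f) × blocked] + 1/6 × blocked.

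Example, f = 0.25, w = 0: comparator = 5/6 × (0.0566 + 0.1070) + 0.0238 = 0.160. Odds ratio = (0.1426/0.8574)/(0.160/0.840) = 0.87.

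| Case | s | g | Wait: eptinezumab v comparator | OR | p<0.05 | Half withdraw | OR | p<0.05 |
|---|---|---|---|---|---|---|---|---|
| A | 0.25 | 0.5 | 14.3% v 15.1% | 0.93 | 5% | 9.4% v 10.8% | 0.86 | 6% |
| B | 0.5 | 0.5 | 14.3% v 16.0% | 0.87 | 6% | 9.4% v 12.1% | 0.75 | 10% |
| C | 0.5 | 0 | 14.3% v 17.7% | 0.77 | 10% | 9.4% v 14.9% | 0.59 | 22% |

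Rejection rates use the arcsine approximation at 100 per arm; 200,000 simulated two-proportion tests agree.

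**Withdrawn in order to switch, eptinezumab arm, w = 0.5:** w[(1 − q²) + q³(1 − q²)] = 0.5 × (0.0975 + 0.0836) = 9.1%.

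**Sensitivity.**

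- f = 0 (no SC user wants another SC drug): 1.00.
- h from 2% to 10%, waiting: B 0.88 to 0.87, C 0.78 to 0.76.
- Chronic-migraine share 30% to 70%, waiting: B 0.86 to 0.88, C 0.76 to 0.79.
- 10% of eptinezumab and Botox users skip the week-12 dose and may change later (add 0.10 × q³(1 − q²)), waiting: A 0.99, B 0.92, C 0.82.
- A share u of wishes in every arm goes to non-study preventives, open to all under Protocol 6.1 (rate = (1 − u) × rate above + u × free). With u = 25% to 50%, waiting: B 0.91 to 0.94, C 0.84 to 0.89.
- SC users' wish is 4%, others 5%, waiting: A 1.14, B 1.07, C 0.95.

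A second model with a constant hazard (20% wish by day 168, all-monthly dosing, all early wishers wait) gives 0.87 and 0.77 for s = 0.25 and 0.5, the same direction.

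**The case against.** Much of the case on the other side stands.

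- **Some exits would be counted.** A reader might infer that withdrawals made in order to switch are never counted. The documents do not say so. Withdrawing participants are asked to attend an Early Termination visit, recorded on the Visit 8 forms (Protocol 8.9, SAP 3.3), and concomitant medication is reviewed there (Protocol 8.8). A new drug already recorded at that visit meets the endpoint. The gap is confined to a drug started after the last contact, or a refused visit. Nor is it right that no listed reason fits: participant or physician request would cover such an exit, without identifying it.
- **The larger effects strain the plan's expectations.** The half-withdraw cases put 9.1% of the eptinezumab arm out for this reason alone, while SAP 15.1 expects loss to follow-up similar to the under-10% seen in the earlier trials. A reader might go further and take every SC wish as SC-to-SC with all-monthly dosing, which gives 0.40 and 60% rejection with half withdrawing. Nothing in the documents supports that combination.
- **Moderate cases are close to nominal.** Rejection is 5% to 6% in A and B when participants wait, and the 95% interval at 100 per arm spans roughly 0.46 to 2.2 times the odds ratio.
- **An equal wish to switch is doubtful.** SC users choose their own product; eptinezumab and Botox are assigned. A slightly lower SC wish reverses A and B.
- **Permitted switching is part of the strategies compared,** dosing interval included. Neither document reads the odds ratio as persistence, and Protocol 3.3 calls all objectives exploratory.

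None of this removes the asymmetry in the rules or supplies a way to identify withdrawal-to-switch.

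**Conclusion.** The concern holds in a limited form. Followed exactly, the plan can give a week-24 switching odds ratio below 1 with equal drugs, because monthly SC-to-SC changes are permitted when eptinezumab and Botox changes are not, and because some withdrawals made in order to switch can be scored as continued index therapy.

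The size rests on assumptions: about 0.93 to 0.77 if blocked participants wait, and 0.86 to 0.59 if half withdraw with none captured, which is an upper-end case. Changes to non-study preventives shrink the gap. Direction is not guaranteed either: the gap is nil with no SC-to-SC wishes and can reverse if SC users wish to switch less.

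The conclusion that this test will falsely favour eptinezumab is not supported. What is supported is that the odds ratio cannot be read as a difference in persistence without knowing the permitted windows and the uncounted exits. The harm is a misread exploratory comparison, not a failed primary result. It is worth fixing because the remedy is cheap.

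**What to change.** Change the analysis only and leave the switching rules as they are.

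1. Add a coded flag, withdrawn in order to change preventive treatment, to the termination reason that sites already select (Protocol 8.9) and the SAP already tabulates (SAP 6.2). In every arm, report the composite of switch or withdrawal-to-switch beside the SAP endpoint, with unknown status counted as switched as the opposite bound to SAP 18.9. For forms already completed, classify from the recorded reasons by a pre-written rule, masked to arm where the text allows; some text will reveal the arm.
2. Carry the protocol's product-level definition into SAP 11.2.1, and describe SC-to-SC and between-class switches separately. The definition matters: if index therapy were read as the SC class, case C (waiting) would have comparator switching of 5/6 × 0.5 × 0.1426 + 1/6 × 0.1426 = 8.3%, and the odds ratio would move from 0.77 to about 1.8.
3. State that the week-24 odds ratio partly reflects unequal permitted windows and is not to be read as a difference in persistence.

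With half withdrawing, item 1 adds the captured share of w[(1 − q²) + q³(1 − q²)] to the blocked rate. Full capture moves the odds ratio from 0.75 to 0.94 (B) and from 0.59 to 0.89 (C); half capture gives 0.87 and 0.76. It does nothing for participants who wait, so item 3 is needed as well.

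The cost is one coded reason or a rule-based review, one derived variable, one bound and some SAP wording. The composite goes beyond the SAP 11.2.1 definition, which is why the SAP endpoint must stay beside it. The eptinezumab figure will look less favourable.
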